5.4. Statistical Analyses

Statistical analysis of this study will be the responsibility of Lilly or its designee.

Unless otherwise specified, the statistical summaries on Phase 1a will be performed by dose levels for Part A and Part B, respectively. For dose expansion phase, the analyses will be performed on patients by treatment arms (monotherapy and combination therapy) for each tumor type of TNBC and GC, and on all patients in the TIL-selected cohort D3.

Any change to the data analysis methods described in the protocol will require an amendment **ONLY** if it changes a principal feature of the protocol. Any other change to the data analysis methods described in the protocol, and the justification for making the change, will be described in the clinical study report (CSR). Additional exploratory analyses of the data will be conducted as deemed appropriate.

5.4.1. Analysis Population

For purposes of analysis, the following populations are defined:

Population	Description
Enrolled	All participants who sign informed consent
Biomarker	All enrolled patients from whom a valid assay result has been obtained
Pharmacokinetic	All enrolled patients who have received ≥ 1 full dose of LY3435151 and have baseline and ≥ 1 postbaseline evaluable PK sample
Intent-to-Treat	All patients who are randomized (enrolled) to study treatment. Patients will be grouped according to randomized treatment. This ITT population will be used for all baseline and efficacy analyses.
Safety	All randomized (enrolled) patients who have received ≥ 1 dose of LY3435151, regardless of their eligibility for the study. Patients will be grouped according to treatment received in Cycle 1. The safety population will be used for all dosing/exposure and safety analyses.
DLT-evaluable	All treated patients who have completed 2 cycles (6 weeks) of treatment (having taken at least 75% of the planned doses of LY3435151) or have discontinued treatment due to a DLT.

Abbreviations: DLT = dose-limiting toxicity; ITT = intent-to-treat; PK = pharmacokinetics.

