9.2. Sample Size Determination

The primary objective of this study is to assess the safety and tolerability of LY3435151, thereby identifying and confirming the RP2D of LY3435151, to be administered as monotherapy and in combination with pembrolizumab, in patients with solid tumors associated with high TIL positivity. The secondary objective is to evaluate PK and any observed evidence of clinical efficacy.

With at least 3 patients treated at the RP2D in the dose-escalation phase and additional patients treated at the RP2D in the dose-expansion phase, a total of at least 20 patients can provide adequate precision for the estimated incidence rate of the following quantities of interest:

- (1) patients having a specified AE, or
- (2) patients showing a response (partial response [PR]/CR) to treatment.

In the dose-expansion phase for both TNBC and gastric adenocarcinoma, approximately n=16 patients in each of these 2 tumor types will be randomized with 1:1 ratio to receive LY3435151 as monotherapy or in combination with pembrolizumab (Stage 1). The sample size of n=16 in each tumor type is required to evaluate the PK/PD and safety data between monotherapy and combination therapy. Following the randomization stage, approximately additional 32 patients in each of the 2 tumor types will be enrolled to receive LY3435151 in combination with pembrolizumab (Stage 2). At each interim analysis for TNBC and gastric adenocarcinoma, clinical data from approximately 20 patients in combination dose expansion (8 from Stage 1 and 12 from Stage 2) will be available to evaluate the antitumor activity of the combination therapy. If the interim results suggest continuation of enrollment for the evaluated tumor type in TNBC and gastric adenocarcinoma, additional patients will be enrolled to receive combination therapy until approximately 32 patients in Stage 2 to achieve a total of approximately n=40 patients for the evaluation of antitumor activity of combination therapy in the corresponding tumor type.

In the dose-expansion phase for other tumor types associated with TIL positivity, the sample size of N=30 in combination therapy provides data to evaluate the safety and PK/PD profile, and to potentially assess the antitumor activity of LY3435151 in combination with pembrolizumab in tumor types other than TNBC and gastric adenocarcinoma.

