5.4.8.1. Primary Efficacy Analyses

The **ORR** is defined as the number of patients who achieve a best overall response of CR or PR divided by the total number of patients treated (safety population). The ORR, with 95% CI, will be summarized for each study part. Per RECIST 1.1 criteria, ORR for the single arm treatment within each tumor type will be calculated by confirmed best responses. Therefore, best overall response will be determined from a sequence of response assessments. Two objective status determinations of CR before progression are required for a best response of CR. Two determinations of PR or better before progression, but not qualifying for a CR, are required for a best response of PR. In the case of SD, measurements must have met the SD criteria at least once after study entry at a minimum interval not less than 6 weeks \pm 7 days measured from study entry.

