5.4.8.2. Secondary Efficacy Analyses

The **disease control rate (DCR)**, defined as the proportion of patients who achieved a CR or PR or stable disease (SD) out of all patients treated, will also be summarized. Per RECIST 1.1 criteria, DCR for the single arm treatment within each tumor type will be calculated by confirmed best responses. See above for the details on the calculation of best responses with confirmation.

The **DoR** is defined as the time from the date measurement criteria for CR or PR (whichever is first recorded) are first met until the first date of objective progression is observed, per RECIST 1.1 criteria, or the date of death. If a responder is not known to have died or have objective progression, then the patient will be censored at the date of last evaluable tumor assessment.

Progression-free survival is defined as the time from the date of start of treatment to the first date of the observed clinical or radiologically documented progressive disease or death due to any cause, whichever occurs first. For patients who are not known to have died or progressed as of the data inclusion cut-off date, PFS time will be censored at the date of the last objective progression-free disease assessment prior to the date of any subsequent systematic anticancer therapy. See [Table JZIA.5.2](#) for details.

Table JZIA.5.2. Progression-Free Survival Event/Censoring Scheme

Situation ^a	Event/Censor	Date of Event or Censor
Tumor progression or death	Event	Earliest date of progressive disease or death
No tumor progression and no death	Censored	Date of last adequate tumor assessment, per RECIST 1.1, or date of first dose (whichever is later) ^b
Unless		
No baseline radiologic tumor assessment available	Censored	Date of first dose
No adequate postbaseline tumor assessment available and death reported after 2 scan intervals following the first dose ^{b,c}	Censored	Date of first dose
Tumor progression or death documented immediately after 2 or more scan intervals following last adequate tumor assessment or randomization (whichever is later) ^{b,c}	Censored	Date of last adequate tumor assessment, per RECIST 1.1, or date of first dose (whichever is later) ^b
New therapeutic anticancer treatment started prior to tumor progression or death	Censored	Date of last adequate radiological assessment prior to new therapeutic anticancer therapy ^b

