Abbreviations: CR = complete response; PR = partial response; RECIST = Response Evaluation Criteria in Solid Tumors; SD = stable disease.

^a Symptomatic deterioration (that is, symptomatic progression that is not confirmed per RECIST 1.1) will not be considered as tumor progression.

^b Adequate tumor assessment per RECIST 1.1 refers to an assessment with 1 of the following responses: CR, PR, SD, or progressive disease.

^c Refer to the statistical analysis plan for the definition of 2 scan intervals, including any adjustment for scan window.

Time to response (TTR) is defined as the time from the date of start of treatment to the date measurement criteria for confirmed CR or PR (whichever is first recorded) are first met. For patients who are not known to have achieved CR or PR as of the data inclusion cut-off date, TTR will be censored at the date of the last objective disease assessment prior the date of any subsequent systematic anticancer therapy.

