5.4.8.3. Exploratory Efficacy Analyses

Overall survival, as well as the efficacy parameters based on iRECIST, will also be analyzed as the exploratory objectives.

The efficacy parameters based on iRECIST will also be analyzed as the exploratory objective.

Overall response rate (iORR) is measured by the percentage of patients who achieved a iCR or iPR as their best overall response (iBOR) out of all treated patients (safety population). The

iBOR is defined as the best response across all time point assessments based on RECIST 1.1 and iRECIST.

Progression-free survival (iPFS) should be the date of randomization (the date of first dose for single-arm study) to the date at which progression criteria are first met (that is, the date of first unconfirmed progression [iUPD]) provided that iUPD or a sequence of consecutive iUPDs is confirmed by a confirmed progression (iCPD), the iUPD followed by only iUPDs at subsequent assessments, no more tumor assessments, or to the death date from any cause in the absence of progressive disease. Patients known to be alive and without the iUPD as mentioned above as of the data inclusion cut-off date for a particular analysis will be censored at the time of the last adequate tumor assessment (a detailed iPFS event/censoring scheme is provided in the table below).

Table JZIA.5.3. Progression-Free Survival (iPFS) Event/Censoring Scheme

Situation ^a	Event/Censor	Date of Event or Censor
iUPD confirmed at next assessment (iCPD) or consecutive iUPD followed by an iCPD	Event	(First) iUPD date
iUPD followed by only iUPD at subsequent assessments and no further tumor assessment available.	Event	First iUPD date of the consecutive iUPDs
iUPD without subsequent assessment	Event	iUPD date
Death	Event	Death date if no iUPD date as in the above 3 situations before death.
No Death and no iUPD or iUPD is followed by iSD/iPR/iCR/	Censored	Date of last adequate tumor assessment per iRECIST, or date of randomization (first dose for single-arm study) (whichever is later) ^b
Confirmed iUPD (iCPD) or death reported after 2 scan intervals following the last adequate tumor scan	Censored	Date of last adequate tumor scan prior to confirmed iUPD (iCPD) or death
No baseline radiologic tumor assessment available	Censored	Date of randomization (first dose for single-arm study)

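### SAP 5.4.1 assigns all efficacy to an ITT set and limits the safety set to patients dosed with LY3435151, which conflicts with the SAP's own endpoint and safety sections and with the protocol

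*SAP*

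**What the plan says.** **Efficacy set.** SAP 5.4.1 defines ITT as everyone randomized or enrolled to study treatment, dosed or not, grouped by randomized treatment, and adds: "This ITT population will be used for all baseline and efficacy analyses". The endpoint sections use other sets:

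- SAP 5.4.8.1: ORR is the number of responders "divided by the total number of patients treated (safety population").
- SAP 5.4.8.2: DCR is "the proportion of patients who achieved a CR or PR or stable disease (SD) out of all patients treated".
- SAP 5.4.8.3: iORR counts patients with iCR or iPR "as their best overall response (iBOR) out of all treated patients (safety population").

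Protocol 9.3 lists no ITT population. Protocol 9.4.1 places efficacy and safety on participants with at least one dose, and Protocol 9.4.3.1 divides ORR by treated patients.

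**Time origins.** In SAP 5.4.8.2, "Progression-free survival is defined as the time from the date of start of treatment", and TTR "is defined as the time from the date of start of treatment to the date measurement criteria for confirmed CR or PR". In SAP 5.4.8.3 the iPFS origin "should be the date of randomization (the date of first dose for single-arm study").

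**Safety set.** SAP 5.4.1 requires at least one dose of LY3435151 and groups patients by the treatment received in Cycle 1. SAP 5.4.7 and Protocol 9.4.4 evaluate anyone given at least one dose of any study therapy, and the Protocol 9.3 safety population requires one dose of study treatment. Protocol 6.1 gives pembrolizumab first in the combination cohorts, with LY3435151 following 30 to 60 minutes later.

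**Baseline set.** SAP 5.4.1 assigns baseline analyses to ITT. SAP 5.4.3.1 summarizes baseline characteristics for all enrolled patients, and SAP 5.4.1 defines enrolled as having signed consent. Protocol Appendix 7 defines enrolled as assigned to a treatment.

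**The concern.** A plan needs one denominator for each table. Here two kinds of patient are handled differently depending on which sentence is followed.

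The first is a patient assigned to treatment but never dosed. Protocol 7.3 foresees this case, because it seeks vital status for randomized participants who did not receive investigational product. Such a patient is in the ITT set but outside the denominators of SAP 5.4.8, and has no start-of-treatment date from which PFS or TTR could run.

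The second is a patient in Part B or D who receives pembrolizumab but stops before LY3435151. This patient is in the protocol's safety population and is evaluated under SAP 5.4.7, but is outside the SAP 5.4.1 safety set and fits no obvious Cycle 1 treatment group. Safety is the primary objective, and a patient who stops between the two infusions may well have stopped because of an early reaction.

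A lesser issue is that a cohort containing both randomized and non-randomized patients could have two iPFS origins in one Kaplan-Meier curve.

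**Working it through.** **1. Who is counted under each rule**

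| Patient | SAP 5.4.1 ITT | SAP 5.4.1 Safety | SAP 5.4.7, Protocol 9.3 and 9.4.4 |
|---|---|---|---|
| Received LY3435151 | in | in | in |
| Part B/D, pembrolizumab only | in | out | in |
| Assigned, never dosed | in | out | out |

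The rules agree only on the first row. Parts A and C have no second row, because LY3435151 is the only study drug there.

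**2. The plan's own interval figures.** Table JZIA.5.1 uses 2-sided 95% Clopper-Pearson limits: lower = Beta quantile 0.025 (x, n−x+1), upper = Beta quantile 0.975 (x+1, n−x).

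- 5/20 gives 0.0866 to 0.4910 (table: 0.09, 0.49).
- 10/40 gives 0.1269 to 0.4120 (table: 0.13, 0.41).
- All ten rows reproduce to two decimals.

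**3. Effect of the denominator on ORR.** Let k be the number of patients in the wider set but not the narrower one, none of them a responder. The rate is x/N in the wider set and x/(N−k) in the narrower. The documents give no value for k, so k = 0 to 4 (k = 0 to 2 in the small arm) is an assumption.

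| Example | k = 0 | k = 1 | k = 2 | k = 4 |
|---|---|---|---|---|
| 10 responders, N = 40 (combination cohort) | 25.0% (12.7–41.2) | 10/39 = 25.6% (13.0–42.1) | 10/38 = 26.3% (13.4–43.1) | 10/36 = 27.8% (14.2–45.2) |
| 2 responders, N = 8 (Stage 1 arm) | 25.0% (3.2–65.1) | 2/7 = 28.6% (3.7–71.0) | 2/6 = 33.3% (4.3–77.7) | not shown |

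**4. Effect on a safety table.** Suppose one of 40 combination patients received only pembrolizumab, and an adverse event occurred in that patient alone.

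- Any-study-treatment set: 1/40 = 2.5%, upper limit 13.2%.
- SAP 5.4.1 set: 0/39 = 0%, upper limit 9.0%.

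**5. iPFS origins.** Stage 1 randomizes about 16 patients per tumor type. Protocol 9.2 continues: "Following the randomization stage, approximately additional 32 patients in each of the 2 tumor types will be enrolled", all to combination therapy. Cohort D3 adds about 30 patients without randomization.

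- Randomized: 2 × 16 = 32.
- Not randomized: 2 × 32 + 30 = 94. Check: 32 + 94 = 126, the planned Phase 1b total, and 94/126 = 75%.
- Randomized share of D1 or D2: 8/40 = 20%.

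Protocol 4.1.2 lets C1 and C2 accrue once the monotherapy RP2D is chosen. It starts randomization only after the combination RP2D is chosen and ends it when 8 patients have accrued to C1 and C2. Any monotherapy patient who enters before randomization opens leaves fewer to randomize. So 32 of 126 and 8 of 40 are maxima, 94 of 126 is a minimum, and mixed origins are possible in C1 and C2 as well.

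**The case against.** The best defence is that the specific rules override the general one. SAP 5.4.8 names treated patients for ORR, DCR and iORR, Protocol 9.4.1 and 9.4.3.1 agree, and the protocol has no ITT set. On that view one stray sentence in SAP 5.4.1 is out of line and the answer is visible. For those three endpoints this largely stands: a reader might infer that the analyst is free to pick a denominator after seeing the data, and the documents do not go that far. The defence does not cover PFS, TTR or OS, whose definitions name no population and therefore stay on ITT by default. Nor does the SAP say that its endpoint denominators are exceptions.

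On safety, the case is narrow. The patient must stop before LY3435151 starts. Protocol 6.6 also allows the other drug to continue, after sponsor consultation, when an infusion reaction is clearly due to one drug. A reader might infer that the event would vanish from reporting. It would not: SAP 5.4.7 evaluates and lists anyone given study therapy. What is lost is the event's place in the summary tables and their denominator.

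On iPFS, a reader might infer that most Phase 1b patients lack a time origin. They do not, because SAP 5.4.8.3 supplies first dose for a single-arm study. What remains is a possible gap between randomization and first dose, whose size the documents do not give, in an exploratory endpoint.

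**Conclusion.** The contradictions are real and should be corrected. Followed literally, SAP 5.4.1 gives PFS and TTR a set that can include patients with no start date, and it drops a pembrolizumab-only patient from summary tables that serve the primary objective.

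The numerical effect is modest and rests on an assumed count. With no undosed or pembrolizumab-only patient it is zero. With one, the ORR example moves by 0.6 percentage points in a 40-patient cohort and 3.6 points in an 8-patient arm, and the upper limit for an event seen only in that patient falls from 13.2% to 9.0%.

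A reader might infer that a decision could be reversed, but the documents do not support this. SAP 5.2.1 specifies no formal test of response rate, and no numerical threshold is set. The interim review is triggered when efficacy and PK/PD data from about 20 patients are available, so no shift at the interim is claimed either. The mixed iPFS origin is secondary.

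**What to change.** - **SAP 5.4.1, Safety:** define it as at least one dose of any study treatment, as in Protocol 9.3. State that a pembrolizumab-only patient in Part B or D is tabulated in the assigned combination cohort. The documents do not dictate this placement, so it needs to be written down.
- **SAP 5.4.1, efficacy:** replace the sentence assigning efficacy to ITT with all treated patients for the efficacy endpoints, and with responders in that set for DoR and iDoR. Group by assigned cohort, since randomized treatment has no meaning for Parts A and B, Stage 2 or D3.
- **Time origin:** use first dose for iPFS in SAP 5.4.8.3 and Table JZIA.5.3, matching PFS. In the PFS censoring row for progression or death after two or more scan intervals (SAP Table JZIA.5.2 and the Protocol 9.4.3.2 table), replace the reference to randomization with first dose.
- **Baseline:** name one population in both SAP 5.4.1 and 5.4.3.1, and settle whether enrolled means consented or assigned to treatment.
- **Optional:** show OS for all randomized patients as well, since Protocol 7.3 seeks their vital status even if they were not dosed.

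The cost is wording in the SAP and in one protocol table row. No extra patients, visits or data are needed.

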5.4.2. Patient Disposition

All patient discontinuation data collected on the electronic case report form will be listed, including the extent of the patient's participation in the study. If known, a reason for discontinuation from treatment and from the study will be listed and summarized. All patients entered in the study will be included in the summary and listing.

All significant protocol deviations will be listed by predetermined categories.

5.4.3. Demographics and Baseline Characteristics

5.4.3.1. Demographics and Disease Characteristics

Patient demographic and baseline characteristics will be summarized and listed for all enrolled patients. At a minimum, sex, age, race, basis for initial diagnosis, initial pathological diagnosis, stage at initial diagnosis, baseline Eastern Cooperative Oncology Group performance status, height, and weight will be summarized. For some subsets of patients, intermediate and study entry pathological diagnosis data will also be listed.

5.4.3.2. Historical Illnesses and Prior Therapies

Historical illnesses are events in the past that ended before the date informed consent is signed. Historical illnesses (coded according to the Medical Dictionary for Regulatory Activities [MedDRA]) will be listed for all enrolled patients.

Prior therapies, including systemic therapy, radiotherapy, and surgeries will be listed for all enrolled patients. Prior radiotherapy and systemic therapy will be summarized by the number of patients with at least 1 of each type of treatment, as well by reason for regimen (for example,

palliative, curative, etc.). Additionally, the number of regimens of prior systemic therapy and, where available, the reason for prior regimens will be summarized.

5.4.4. Concomitant Therapy

Concomitant medications will be summarized and listed for the safety population.

5.4.5. Postdiscontinuation Therapy

The numbers and percentages of patients reporting postdiscontinuation therapies will be provided overall, by type of therapy (surgery, radiotherapy, or systemic therapy), and by drug name.

5.4.6. Exposure

The following exposure-related variables will be reported using summary by phase and treatment group:

- exposure: duration of treatment, number of cycles received, number of patients completing ≥ 1 cycle, ≥ 2 cycles, ..., x cycles, mean, and standard deviation
- reasons for dose modification (delays, omissions, and reductions, scheduling conflict, and AE summarized by preferred term [PT])
- dose intensity: weekly dose intensity and relative dose intensity

Details of study drug administration will be included in patient listings.

5.4.7. Safety Analyses

All patients who receive at least 1 dose of any study therapy will be evaluated for safety and toxicity.

Safety measures that will be used in the study include AEs, DLT (defined in protocol) in dose escalation phase, clinical laboratory test results and vital signs. The MedDRA Version 22.0 (or higher) will be used when reporting AEs by MedDRA terms. A treatment-emergent adverse event (TEAE) is defined as an event that first occurred or worsened in severity between the first dose of study treatment and 30 days after the last dose of study treatment and related serious AEs (SAEs) reported beyond 30 days after the last dose of study treatment. Immune-related adverse event (irAE) is also indicated in the database and will be summarized in the safety analysis.

Safety analyses will include summaries of the following:

- DLTs at each dose level in Part A and Part B
- AEs, including severity and possible relationship to the study drug
- DLT-equivalent AEs, including severity and possible relationship to the study drug
- SAEs, summarized by PT and repeated for events deemed by the investigator to be possibly related to study treatment

- irAEs, summarized by PT and repeated for events leading to dose delays or omissions, for events leading to discontinuations from study treatment, and for events leading to death
- AEs leading to dose delays or omissions, summarized by PT
- AEs leading to discontinuations from study treatment, summarized by PT and repeated for events deemed by the investigator to be possibly related to study treatment
- AEs leading to death, summarized by PT and repeated for events deemed by the investigator to be possibly related to study treatment
- reasons for deaths, summarized for all deaths, deaths on therapy, and deaths within 30 days of treatment discontinuation
- treatment-emergent abnormal changes in laboratory values
- treatment-emergent abnormal changes in vital signs and electrocardiograms
- Listings of all AEs, TEAEs, SAEs, and deaths will also be provided.
- Listings of all laboratory data will be provided with a flag for values outside of the laboratory normal. Abnormal results will be listed separately for all enrolled patients.

